2.4. Statistical Hypotheses

2.4.1. Hgb efficacy Co-Primary Hypothesis

The co-primary Hgb efficacy objective will assess the estimand defined as the effect of daprodustat treatment relative to darbepoetin alfa on the change in Hgb from baseline to the average of all values in the EP, regardless of adherence to treatment including interruptions and discontinuations, the use of non-randomized ESA medication for any reason including rescue therapy, or the use of blood transfusions, in non-dialysis subjects with anemia secondary to CKD and assuming subjects do not die before the end of the EP. The analysis will test whether daprodustat is non-inferior to darbepoetin alfa according to the following statistical hypotheses:

- **Null:** The difference in mean change in Hgb between baseline and EP, between treatment arms (daprodustat – darbepoetin alfa), is less than or equal to -0.75 g/dL.
- **Alternative:** The difference in mean change in Hgb between baseline and EP, between treatment arms (daprodustat – darbepoetin alfa), is greater than -0.75 g/dL

The non-inferiority margin is pre-defined as -0.75 g/dL; determined based upon a combination of clinical judgment, statistical reasoning and regulatory guidance for designing non-inferiority trials.

Statistical significance of non-inferiority will be assessed at the one-sided 2.5% level. An ANCOVA model including prognostic randomization stratification factors (region and current ESA use) and factors for baseline Hgb and treatment will be used to obtain a point estimate and two-sided 95% CI for the treatment difference (daprodustat – darbepoetin alfa) and generate the corresponding p-value for the non-inferiority test. Non-inferiority will be established if the lower limit of the two-sided 95% CI for the treatment difference is greater than -0.75 g/dL.

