7.1.2. Planned Hgb Efficacy Co-Primary Statistical Analyses

The co-primary efficacy estimand is the effect of daprodustat relative to darbepoetin alfa on the change in Hgb from baseline to the average of all values in the EP, regardless of adherence to treatment including interruptions and discontinuations, the use of non-randomized ESA medication for any reason including rescue therapy, or the use of blood transfusions, in non-dialysis subjects with anemia secondary to CKD and assuming subjects do not die before the end of the EP.

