7.1.2.4. Strategy for Intercurrent (Post-Randomization) Events

The following are the intercurrent events for the primary efficacy analyses:

- Death prior to the end of the EP (i.e. before Week 52 visit)
- Randomized treatment interruption or discontinuation prior to the end of the EP
- Use of non-randomized ESA medications for any reason including rescue prior to the end of the EP

- Receipt of blood transfusions prior to the end of the EP

Except for the intercurrent event of death prior to the end of the EP, a treatment policy strategy will be used in which all Hgb data recorded during the EP (Weeks 28-52) will be included in the primary efficacy analysis, regardless of discontinuation or interruption of study medication due to any reasons, and regardless of receipt of non-randomized ESA medications for any reason including rescue, or blood transfusions. For deaths, a hypothetical strategy will be used as described in Section 7.1.2.

The following are causes of missing Hgb data affecting the co-primary efficacy endpoint that are not due to intercurrent events:

- Study withdrawal prior to the end of the EP
- Permanent switching from clinic visits to remote visits prior to the end of the EP
- Intermittent missing Hgb values at one or more visits with the EP

Missing data will be imputed as described in Section 7.1.2.

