7.1.2.5. Statistical Analyses/Methods

Hgb Efficacy Co-Primary Statistical Analyses
Endpoint(s)

 • Mean change in Hgb between baseline and EP
Model Specification

 • Hgb during the EP will be defined as the mean of all available post-randomization Hgb values (on and off-treatment) during the EP (Week 28-52). • The ANCOVA model used to quantify the difference in mean Hgb change will adjust for the following baseline values: 
 ○ Treatment ○ Baseline Hgb (see Section 10.5.2) ○ Current ESA use (as randomized, see Section 10.10.2) ○ Region (as randomized, see Section 10.9 & Section 10.10.2)
Multiple Imputation Analysis

 • Multiple imputation analysis will be performed using all available Hgb values (on and off-treatment) and conducted under a set of assumptions about missing Hgb values (see Section 10.6.3). 
 ○ Intermittent missing post-baseline scheduled Hgb data in both arms through Week 52 will be imputed using PROC MI procedure with NIMPUTE = 200 and MCMC IMPUTE = monotone to generate 200 datasets with only monotone missing patterns. Burn in iterations (NBITER) and maximum iteration (MAXITER) will both be set to 500. The seed for reproducibility is set to 200808. The imputations will be done by randomized treatment, current ESA use at randomization, and region. ○ For each of the monotone missing dataset (out of the 200 imputed as indicated above), the missing scheduled Hgb values through Week 52 will be imputed based on the MAR assumption and will be performed using PROC MI by treatment, current ESA use at randomization, and region. The monotone regression will have baseline Hgb, prior scheduled (possibly imputed) Hgb values, and may include current ESA use at randomization and region as covariates (see Model Checking & Diagnostics, below).

Hgb Efficacy Co-Primary Statistical Analyses

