
 ● All available observed Hgb values (on and off-treatment) will be summarized using mean, standard deviation, minimum, P25, median, P75 and maximum at each visit by treatment group. In addition to scheduled visits, the baseline value and mean MP, mean EP, mean Alt EP, and end of treatment values will be included (see Section 10.6.3). This summary is repeated by current ESA use at randomization. 
 ○ This summary of Hgb will also be repeated for visits up to and including Week 52, using the data used for the primary Hgb analysis (i.e., including imputed values (see Section 10.6.3)), and by current ESA use at randomization. ● All available observed Hgb change from baseline values (on and off-treatment) will also be summarized using mean, standard deviation, minimum, P25, median, P75, and maximum at each post-baseline visit, including the mean MP, mean EP, mean Alt EP, and end of treatment values (see Section 10.6.3). This summary is repeated by current ESA use at randomization. 
 ○ This summary of Hgb will also be repeated for visits up to and including Week 52, using the data used for the primary Hgb analysis (i.e., including imputed values (see Section 10.6.3)), and by current ESA use at randomization. ● The number and percentage of subjects with imputed data in the primary Hgb analysis will be provided by treatment group. The number and percentage of subjects by reason for data imputation will be provided. Reasons include: intermittent missing Hgb values, death before Week 28, death during Weeks 28 – 52, investigator site closed before Week 28, investigator site closed during Weeks 28-52, lost to follow-up before Week 28, lost to follow-up during Weeks 28 – 52, consent withdrawn before Week 28, consent withdrawn during Weeks 28 – 52, EOS visit occurred before Week 28, EOS visit occurred during Weeks 28-52, and other monotone missing Hgb values. Subjects will be further classified as either having observed all 7 scheduled EP Hgb values, having observed a partial schedule of EP Hgb values, having observed no scheduled EP Hgb values with at least one unscheduled EP Hgb value, or having observed no EP Hgb values, scheduled or unscheduled. For subjects with partial scheduled EP Hgb values, both the pattern of imputed data (intermittent, monotone) and the amount of imputed data (1 – 6 scheduled Hgb values missing) will be summarized. For subjects with partial scheduled EP Hgb values and a monotone imputed data pattern, the reason for the monotone imputed scheduled EP Hgb values will be provided. Reasons include: death during Weeks 28-52, investigator site closed during Weeks 28-52, lost to follow-up during Weeks 28 – 52, consent withdrawn during Weeks 28 – 52, EOS visit occurred during Weeks 28-52, and other monotone imputed Hgb values. And for summaries of the amount of missing scheduled EP Hgb values, the presence or absence of additional unscheduled EP Hgb values will be summarized.

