
Hgb Efficacy Co-Primary Statistical Analyses

- The least square (LS) mean estimates and standard errors by treatment group, LS mean difference, two-sided 95% CI and one-sided non-inferiority p-value for the difference in the co-primary Hgb endpoint between the daprodustat and darbepoetin alfa arms from the ANCOVA model will be presented. The number of subjects contributing to the analysis and the associated mean and standard deviation of the baseline and EP Hgb values will also be displayed with the results of the ANCOVA model.
- The LS mean difference and associated two-sided 95% CI will be displayed on a forest plot together with supportive analysis results (excluding the Tipping Point Analysis).
- All available observed Hgb values (on and off-treatment) will be displayed graphically for each scheduled study visit using a line plot. The line plot of mean values and 95% CIs by time will include horizontal reference lines to depict the Hgb analysis range (10-11.5 g/dL), vertical reference lines to identify the EP (weeks 28-52), and the number of subjects by treatment group contributing to each mean value. The plot will be repeated by current ESA use at randomization.
 - This figure will also be repeated for visits up to and including Week 52, using the data used for the primary Hgb analysis (i.e., including imputed values). (see Section 10.6.3)).
- All available observed Hgb change from baseline values (on and off-treatment (see Section 10.6.3)) will be displayed graphically for each scheduled study visit using a line plot. The line plot of mean values and 95% CIs by time will include vertical reference lines to identify the EP (Weeks 28-52), and the number of subjects by treatment group contributing to each mean value. The plot will be repeated by current ESA use at randomization.
 - This figure will also be repeated for visits up to and including Week 52, using the data used for the primary Hgb analysis (i.e., including imputed values). (see Section 10.6.3)).
- A listing of all hemoglobin values will be provided, including treatment, most recent dose, site ID, unique subject ID, visit, assessment date, select demographic information and central laboratory and HemoCue Hgb values.

Model Results Interpretation

- Non-inferiority will be achieved if the lower limit of the two-sided 95% CI of the treatment difference is greater than the pre-specified non-inferiority margin of -0.75 g/dL.

Sensitivity Statistical Analyses

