
randomized treatment, current ESA use at randomization, and region.
 
 ○ For each of the monotone missing dataset (out of the 200 imputed as indicated above), the missing scheduled Hgb values in both arms through Week 52 will be imputed based on the MAR assumption and will be performed using PROC MI by treatment, current ESA use at randomization, and region. The monotone regression will include baseline Hgb, prior scheduled (possibly imputed) Hgb values, and may have region, and current ESA use at randomization as covariates (see Model Checking & Diagnostics, below). The seed for reproducibility is set to 200808. ○ For each treatment arm separately, the imputed monotone missing Hgb values will vary from the MAR scenario by a multiple of delta, where delta represents a change in Hgb over a 4-week interval. No delta adjustments will be done for intermittent missing values. Beginning with the first missed visit (which could occur before Week 28), for every 4-week interval, the imputed Hgb value would shift an additional delta. For example, the first missed visit will use delta, the second missed visit will use 2*delta, etc. The deltas explored for each treatment arm will range from -4 g/dL to 4 g/dL per 4-week interval with a 0.1 g/dL increment respectively. Delta scenarios which are known ahead of time to not possibly represent the tipping point may not be explored. ○ The low and high cutoffs at Hgb values of 6 g/dL and 15 g/dL will be applied to all imputed Hgb values. ○ EP Hgb values will be computed for each pair of deltas and compared across treatment groups using the co-primary ANCOVA model described above (including unscheduled visit). Rubin's rules [Rubin, 1987] will be used to combine results of the imputed datasets using SAS PROC MIANALYZE procedure. As a result, for each pair of delta values, a single estimated treatment difference and its standard error will be produced, with which a 95% CI will be calculated. ○ Graphics depicting treatment difference and one-sided non-inferiority (NI) p-value surfaces will be produced using an enhanced tipping point approach [Liublinska, 2014].
Model Checking & Diagnostics

 ● Refer to Appendix 12: Model Checking and Diagnostics for Statistical Analyses.
Model Results Presentation

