10.2.1.3. Schedule of Assessments for Subjects Permanently Discontinuing Randomized Treatment

Protocol Activity (Note: All visit timings are relative to Day 1)	Early Treatment Discontinuation Visit (within 2 weeks of discontinuing randomized treatment)	Day 1 through Week 52	
		Week 4, 16, 28, 40, 52 ± 2 weeks ⁷	Unscheduled
IRT system transaction	X		
SBP/DBP, HR	X (triplicate)	X	X
EKG	X		
Iron therapy, transfusions ¹	X	X	X
Urine (serum if transitioned to dialysis) pregnancy test (FRP only)	X ⁸		
HemoCue Hgb	X	X	X
Hematology ³	X	X	
Clinical chemistry ³	X	X	
Ferritin, total iron, UIBC, hepcidin, lipids, iPTH	X		
Hospitalization ¹ , transition to dialysis ¹ , kidney transplant ¹	X	X	X
Non-serious AEs, AEs of special interest, SAEs, clinical events	X	X	X
Review concomitant medications	X	X	X
Healthcare resource utilization (subject-reported)	X		
CKD-AQ. ^{5, 10}	X		
PGI-S, PGI-C ^{5, 10}	X		
SF-36 ^{5, 10}	X		
EQ-5D-5L & EQ-VAS ^{5, 6, 10}	X		
WPAI-ANS-CPV ^{4, 5, 10}	X		
ADPKD subjects only: Ultrasound	X ¹²		
ABPM sub-study (Appendix 13): 24 hour ABPM		X (Week 16)	
Record awake and sleep times		X (Week 16) ²	
24 hour urine collection (sodium, aldosterone & creatinine)		X (Week 16) ¹¹	

Schedule of Assessments for Subjects Permanently Discontinuing Randomized Treatment (Continued)

Protocol activity (visits ± 2 week) (Note: All visit timings are relative to Day 1)	Year 2 ⁷				Year 3 ⁷				Year 4 ⁷					Unscheduled	End of Study ⁹
	Week 64	Week 76	Week 88	Week 100	Week 112	Week 124	Week 136	Week 148	Week 160	Week 172	Week 184	Week 196	Week 208		
IRT system call															X
SBP/DBP, HR	X	X	X	X	X	X	X	X	X	X	X	X	X	X	X
HemoCue Hgb	X	X	X	X	X	X	X	X	X	X	X	X	X	X	
Hematology ³	X	Hgb only	X	Hgb only	X	Hgb only	X	Hgb only	X	Hgb only	X	Hgb only	X		X
Clinical chemistry ³	X		X		X		X		X		X		X		X
Hospitalization ¹ , transition to dialysis ¹ , kidney transplant ¹	X	X	X	X	X	X	X	X	X	X	X	X	X	X	X
Non-serious AEs, SAEs, AEs of special interest, clinical events	X	X	X	X	X	X	X	X	X	X	X	X	X	X	X
Review concomitant medications	X	X	X	X	X	X	X	X	X	X	X	X	X	X	X
Transition to dialysis ¹	X	X	X	X	X	X	X	X	X	X	X	X	X	X	X
ADPKD subjects only: eGFR ¹³		X		X		X		X		X		X			

1. Record in eCRF, if applicable.
2. Subject will record sleep and wake time during the ABPM session.
3. See details on hematology and clinical chemistry in Protocol Section 7.4.11.
4. If local dialect or language is available.

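### Co-primary Hgb imputation fills four EP visits that are not scheduled after permanent discontinuation, using no treatment-status term, and so pulls off-treatment Hgb part of the way back toward on-treatment levels

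*SAP*

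**What the plan says.** - **Estimand.** SAP 7.1.2 defines the co-primary Hgb effect "regardless of adherence to treatment including interruptions and discontinuations". Section 7.1.2.4 adds that, for every intercurrent event except death, "a treatment policy strategy will be used in which all Hgb data recorded during the EP (Weeks 28-52) will be included".
- **Schedule on treatment.** SAP 10.2.1.1 has Hgb at Weeks 28, 32, 36, 40, 44, 48 and 52 of the EP.
- **Schedule after permanent discontinuation.** SAP 10.2.1.3 lists "Week 4, 16, 28, 40, 52" for the first year.
- **Imputation.** In 7.1.2.5, "Intermittent missing post-baseline scheduled Hgb data in both arms through Week 52 will be imputed using PROC MI procedure", within randomized arm, ESA use and region. The monotone step that follows uses the same strata with baseline and prior Hgb. Section 10.6.3.1 extends imputation to every missing value through Week 52. The fallback rules in 10.12.1 only coarsen strata or drop covariates. No step contains treatment status.
- **Missing-data table.** Section 7.1.2.5 classes subjects by, among other things, "having observed all 7 scheduled EP Hgb values". Neither its reasons for imputation nor the causes of missing data in 7.1.2.4 mention the shorter off-treatment schedule.
- **Tipping point.** "No delta adjustments will be done for intermittent missing values".
- **Decision rule.** The lower 95% limit must be "greater than the pre-specified non-inferiority margin of -0.75 g/dL".

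**The concern.** A treatment-policy analysis should let Hgb after stopping count in full. Here a subject who stops before Week 28 and then attends every required visit still has four of seven EP values generated by a model. Discontinued subjects have no scheduled Hgb at Weeks 32, 36, 44 and 48, so the model learns how those visits relate to their neighbours from subjects who have not permanently stopped, including some who stop later. A conditional-normal imputation then returns values between the subject's own off-treatment level and the arm's general level. If the arms differ in how many subjects stop, or in how far Hgb moves afterwards, part of that difference disappears from the co-primary estimate. When a later scheduled value exists, these gaps are intermittent and the tipping-point analysis leaves them alone. Separately, the missing-data table will report fully compliant off-treatment subjects as having partial data.

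**Working it through.** **Visit count.** The on-treatment schedules give 28, 32, 36, 40, 44, 48, 52, that is 7, which reproduces the SAP's figure. Off treatment they give 28, 40, 52, that is 3. The share imputed by design for a fully compliant subject who stopped before Week 28 is 4/7 = 57%.

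**Assumptions (none of these is in the SAP).** Unit visit variance. The correlation between visits at weeks t and s is a + (1 − a − e)·ρ^(|t−s|/4), where a is the between-subject share, e the visit-error share and ρ the 4-week correlation of the rest. The off-treatment shift is a step at stopping.

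**Share of the shift kept.** For a stop between Weeks 16 and 28, the observed weeks are O = {0, 4, 16, 28, 40, 52}, with deviation δ = 1 at 28, 40 and 52 and 0 before. The imputed weeks G = {32, 36, 44, 48} have expected deviation Σ_GO Σ_OO⁻¹ δ. The fraction lost from the EP mean is L = Σ(1 − kept)/7.

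| a, ρ, e | kept at 32/36/44/48 | L |
|---|---|---|
| 0, 0.9, 0 | 0.99 each | 0.006 |
| 0, 0.7, 0 | 0.89 each | 0.065 |
| 0.3, 0.7, 0.1 | 0.85/0.86/0.87/0.86 | 0.080 |
| 0.2, 0.6, 0.2 | 0.72/0.73/0.74/0.73 | 0.153 |
| 0.1, 0.5, 0.3 | 0.56/0.57/0.57/0.57 | 0.247 |
| 0, 0.5, 0.2 | 0.55 each | 0.256 |

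Example, fourth row: (4 − 2.92)/7 = 0.154, which agrees up to rounding.

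**Effect on the treatment difference.** With fraction f off treatment and shift s in each arm, bias ≈ −L·(f_dapro·s_dapro − f_darbe·s_darbe). A simulation with within-arm multivariate-normal imputation (1,900 per arm, assumed; three repeats) was run at L = 0.065, 0.080 and 0.247:

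| off treatment, dapro/darbe | shift, g/dL | formula | simulated bias, g/dL |
|---|---|---|---|
| 20%/20% | −1/−1 | 0 | 0.004, 0.004, −0.004 |
| 30%/20% | −1/−1 | 0.10·L = 0.007, 0.008, 0.025 | 0.005, 0.005, 0.022 |
| 30%/20% | −1.5/−0.5 | 0.35·L = 0.023, 0.028, 0.086 | 0.018, 0.027, 0.091 |
| 30%/30% | −1.5/0 | 0.45·L = 0.029, 0.036, 0.111 | 0.021, 0.033, 0.115 |

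In the worst case the true difference was −0.450 and the imputed one −0.336, both well above −0.75. Using observed values only came within 0.01 g/dL of the truth throughout.

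**Stops during the EP.** The same six covariances give the share of the true off-treatment contribution to the EP mean that is kept:

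| stop week | SAP imputation | drop the four visits once off treatment | linear interpolation |
|---|---|---|---|
| 26 | 74–99% | 100% | 100% |
| 30 | 61–83% | 78% | 83% |
| 34 | 67–90% | 70% | 90% |
| 38 | 75–99% | 70% | 100% |
| 42 | 51–66% | 47% | 67% |
| 46 | 65–75% | 58% | 75% |

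Example, stop at Week 38: the true weight is 4/7. Dropping Weeks 44 and 48 leaves 28, 32, 36 (on) and 40, 52 (off), weight 2/5, and (2/5)/(4/7) = 70%. Interpolation between Weeks 40 and 52 restores 4/7.

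**The case against.** The strongest reply is that this hardly matters and is already checked. Section 7.1.2.5 prespecifies an observed-values analysis, on and off treatment without imputation, shown on the same forest plot. For early discontinuers who stay in the study, that is essentially the correction. The bias is small against 0.75 and depends wholly on assumed inputs. This stands, and it limits the weight of the point. It does not justify leaving a known misfit in the co-primary analysis when the remedy is cheap.

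Two stronger readings are tempting, and the document does not support them. A reader might infer that off-treatment Hgb is simply replaced by on-treatment Hgb. It is not: the model conditions on the subject's own Weeks 28, 40 and 52. Nor are the subjects behind those relations all taking drug, because the reduced schedule applies only to permanent discontinuation, and subjects on a dose hold stay on the full one. A reader might also infer that the tipping-point analysis never reaches these visits. If Week 52 is missing too, the trailing gaps are monotone and do receive a delta.

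An objection to the obvious remedies also stands. Dropping the four visits for everyone who stops does worse than the current plan for stops from about Week 38, and in some settings earlier, because it over-weights on-treatment visits. An on/off-treatment indicator is hardly identified, since there are almost no scheduled off-treatment data at those weeks.

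**Conclusion.** The point holds in limited form. The imputation grid does not match the off-treatment schedule and the model has no treatment-status term, so the off-treatment shift is partly shrunk, against the stated strategy. For stops before Week 28 the loss is roughly 5–25% of the shift; it falls below 1% only if visits are very highly correlated with no visit-level error. Bias in the treatment difference is about zero with equal discontinuation rates and shifts, and about 0.02–0.12 g/dL (3–16% of the margin) with strongly unequal shifts. It favours daprodustat if its subjects stop more often or fall further, and the reverse otherwise. The documents do not support a claim that the non-inferiority conclusion is in danger. This should be corrected, but it is not decisive. The mislabelling in the missing-data table holds whatever the size of the bias.

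**What to change.** 1. For subjects who permanently stop before Week 28, remove the imputed Weeks 32, 36, 44 and 48 after imputation. The EP mean then uses Weeks 28, 40 and 52 (observed, or imputed if truly missed) plus unscheduled values.
2. For subjects who stop during the EP, do not apply that filter. Either keep the full grid, or fill the off-schedule visits by linear interpolation between the subject's own values, as 10.6.3.1 already does for time in range.
3. In the missing-data table, count against each subject's own schedule and list the reduced off-treatment schedule as a separate reason.
4. Do not rely on an on/off-treatment indicator in the imputation model.

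Cost: SAP wording and a little programming. Early discontinuers' EP means rest on about 3 values instead of 7. In the Week 28–36 supportive analysis the same rule would leave them Week 28 plus any unscheduled values. The observed-values analysis stays as a supportive check.
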